10.12.3 Study Exit

A study exit eCRF is required for all subjects. Prior to exiting a subject from the study, it is recommended to follow the subject until all ongoing system and/or procedure related AEs are resolved or unresolved with no further actions planned. All data available through the time of the subject's exit will be used for analysis.

MDT17051PDS Version 4.0 Page 31 of 56

Subjects are urged to remain in the study as long as possible but may be exited from the study for any of the following situations:

- Study completed
- Subject lost to follow-up
- Subject death
- Subject did not meet inclusion/exclusion criteria
- Subject was not implanted with a (investigational) device
- Subject did not provide consent <or data use protection authorization>
- Subject chooses to withdraw (e.g., consent withdrawal, relocation to another geographic location)
- Investigator deems withdrawal necessary (e.g., medically justified, inclusion/exclusion criteria not met, failure of subject to maintain adequate study compliance)

If discontinuation is because of safety or lack of effectiveness, the subject may be asked to be followed for collecting safety data outside the clinical investigation.

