9.2 Subject Enrollment

After being informed of the nature of the study, the subject will provide written informed consent that has been approved by the sponsor and the appropriate IRB of the respective clinical site. A minimum of one hundred and twenty-five (125) subjects will be enrolled in the study at a minimum of 4 US sites with competitive enrollment not to exceed 40 subjects per site.

A subject is considered enrolled in the study when:

- it is confirmed that the ICF is signed,
- they meet all pre-operative inclusion criteria,
- they meet no pre- or intra-operative exclusion criteria,
- they have received Parietene™ DS Composite Mesh intraoperatively.

Adverse events will be collected starting at the time of skin incision and the subject must be followed for the full 24 months if the procedure was begun or completed with the study device. If ICF signature occurs more than 30 days before the procedure the subject is to be reconsented. No study procedures will be performed until informed consent form has been completed.

The elective ventral hernia repair procedure will be performed per the intraperitoneal onlay mesh technique (IPOM) by open or laparoscopic approach.

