10.12 Subject Exit, Withdrawal or Discontinuation

10.12.1 Enrolled

A subject is considered enrolled in the study when it is confirmed that the ICF is signed, subject meets all pre-operative inclusion criteria, subject meets no pre- or intra-operative exclusion criteria, and the subject has received Parietene™ DS composite intra-operatively. The subject must be followed for the full 24 months if the procedure was begun or completed with the study device. See section 8.2 for additional details.

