10.12.4 Withdrawal

The reason for study exit will be documented on the applicable eCRFs. In the event the subject withdraws consent during the study, the date of withdrawal will be documented. If the study Investigator(s) voluntarily removes a subject from further study participation, supporting documentation must be in place for the rationale and date of removal. Follow-up of subjects withdrawn will be determined by investigator(s). Withdrawn subjects will be not replaced.

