12.1 Adverse Events

Potential Adverse Events associated with the use of Parietene™ DS composite in ventral hernia repair could include but are not limited to; seroma, hematoma, recurrence, adhesions, bowel obstruction, fistula formation, infection, inflammation, acute and chronic pain, extrusion/erosion and/or allergic reaction to the components of the device. In regard to pain, the following definitions will be used for this study:

- Acute pain (pain that resolves within three months of surgery)
- Chronic pain (pain that lasts more than three months after surgery)

For study purposes, the following occurrences are considered to be unavoidable adverse events as they are expected observations following surgical procedures (primarily associated with anesthesia) and will not be considered reportable AEs, as long as the event is not associated with significant sequelae, does not prolong hospitalization, and responds to standard medical therapy:

- Post-Operative transient nausea determined to be procedure related within the first 24 postoperative hours.
- Post-Operative transient emesis determined to be procedure related within the first 24 postoperative hours.
- Post-Operative constipation determined to be procedure and/or medication related for the duration of medication administration for management of pain.
- Post-Operative pain that the Investigator considers common and within normal limits for the procedure and is well-managed with medication.

All Adverse Events and Device Deficiencies will be collected and documented in the eCRF starting at the time of enrollment for all subjects, up to and including 24 months follow-up and monitored until resolved if possible.

For Adverse Events that require immediate reporting initial reporting may be done by phone, fax, e-mail or on the eCRF, completing as much information as is available. The original fully completed Adverse Event eCRF must be submitted to Medtronic as soon as possible. In addition, Investigators are obligated to report Adverse Events in accordance with the requirements of their IRB.

MDT17051PDS Version 4.0 Page 34 of 56

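### Protocol 10.12.3 and 10.12.4 let an investigator end study follow-up of a subject who already has the mesh, against the 24-month rule, so outcomes after such an exit are not captured

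*Protocol*

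**What the plan says.** **The follow-up rule.** Protocol 10.12.1 states: "The subject must be followed for the full 24 months if the procedure was begun or completed with the study device". Section 9.2 says the same. Section 12.1 has adverse events collected "starting at the time of enrollment for all subjects, up to and including 24 months follow-up and monitored until resolved if possible".

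**The exit rules.** Protocol 10.12.3 lists reasons for exit. One is that the investigator judges withdrawal necessary; besides medical justification, its examples are "inclusion/exclusion criteria not met, failure of subject to maintain adequate study compliance". Nothing limits these to subjects who did not receive the mesh. The section closes with the case where discontinuation is "because of safety or lack of effectiveness, the subject may be asked to be followed for collecting safety data outside the clinical investigation". Section 10.12.4 leaves the follow-up of withdrawn subjects to the investigator and does not replace them. Section 10.12.2.2 stops follow-up at discharge for subjects who fail an intra-operative criterion.

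**The analysis rules.** Protocol 10.12.3 uses all data up to exit. Protocol 14.3.1 counts a recurrence diagnosed within 12 months even in a subject who withdrew before the 12-month assessment. SAP 7.9 divides recurrences within 12 months by those recurrences plus recurrence-free subjects with at least 12 months of follow-up, and applies the same formula at 1, 3 and 24 months. Protocol 14.3.2 keeps subjects with an event in the incidence of adverse device effects (ADEs). Nothing is imputed (Protocol 14.6, SAP 7.4) except within the CCS, whose rules sit in a user guide that is not reproduced.

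**The concern.** The textile is a permanent implant, so there is no study treatment to stop; exit ends observation and nothing else. The study exists to describe recurrence and safety to 24 months, yet a site that follows 10.12.3 can end observation of an implanted subject whom 9.2 and 10.12.1 say must be followed. The study is unblinded (Protocol 10.7.1), so the person deciding may know how the subject is doing.

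If exit is related to prognosis, the subjects who remain are not a fair sample of those implanted. At stake are the 12-month recurrence rate, the later CCS scores, the count of later serious adverse events (SAEs) and serious adverse device effects (SADEs), and the Kaplan-Meier curves, where censoring at exit may be informative.

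**Working it through.** **1. The plan's own figures.** Protocol 14.5 and SAP 6: 100 evaluable subjects and 20% attrition give 100 / (1 − 0.20) = 125, as stated. The half-width 1.96 × √(p(1 − p)/100) is 3.60 points at 3.5% and 4.35 points at 5.2%, matching the stated 3.6 and 4.4.

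**2. The rules side by side.**
- Sections 9.2 and 10.12.1 against 10.12.3 and 10.12.4: the same implanted subject must be followed for 24 months, and may also be exited at the investigator's discretion with later follow-up optional. A site cannot apply both.
- Sections 9.2 and 10.12.1 against 10.12.2.2: if the procedure was begun with the device and an intra-operative exclusion is then met, one rule gives 24 months and the other stops at discharge.
- Section 10.12.5 against 10.12.3: loss to follow-up needs three calls and a certified letter and is not declared until just before database lock. The compliance exit has no such steps.
- Section 16.9: even if the study is suspended, the sponsor and investigators remain bound to complete follow-up of enrolled subjects.
- Enrolment requires that "they meet no pre- or intra-operative exclusion criteria" (9.2), and the Full Analysis Set (FAS) consists of enrolled subjects who received the device. No passage removes a subject found ineligible later, but none says that the subject stays.

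**3. What survives an exit.** A recurrence diagnosed before exit stays in numerator and denominator at 12 months (Protocol 14.3.1, SAP 7.9). At 24 months only the SAP formula secures this, because Protocol 14.3.2 has no matching clause for withdrawn subjects. ADEs recorded before exit are kept.

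**4. What does not.** A recurrence after exit goes unrecorded, and the subject, having less than 12 months of follow-up, leaves the 12-month denominator. CCS at 12 and 24 months is not collected. SAEs and SADEs after exit fall outside the database.

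**5. Size.** The documents give no number of discretionary exits, so the inputs here are assumed. Take 100 subjects who would have been evaluable, 5 with recurrence (5.0%). Exit 5 before any recurrence; k of them would have recurred. The reported rate is (5 − k) / 95:

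| k | Reported rate | Shift from 5.0% |
|---|---|---|
| 0 | 5/95 = 5.3% | +0.3 points |
| 1 | 4/95 = 4.2% | −0.8 points |
| 2 | 3/95 = 3.2% | −1.8 points |

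Break-even: (5 − k)/95 = 5/100 gives k = 0.25, which is 5% of the 5 exits, the overall rate. The report is too low only when exited subjects recur more often than average.

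Seen from the other side, if 5/100 is reported and every exited subject later recurs, 1 such exit means 6/101 = 5.9% and 5 mean 10/105 = 9.5%.

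An outer limit uses all 25 planned losses, whatever their cause. With 5 diagnosed recurrences, the rate in all 125 lies between 5/125 = 4.0% and 30/125 = 24.0%, with break-even at 1.25 hidden recurrences.

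**The case against.** A reader might infer that the worst outcomes drop out of the 12- and 24-month endpoints. The documents do not support that. A subject exited because of a recurrence or an ADE already has the event on record, and Protocol 10.12.3, 14.3.1 and 14.3.2 with SAP 7.9 keep it; the effect on the 12-month rate is nil. Nor is recurrence a listed exit reason: safety and lack of effectiveness appear only in a conditional closing sentence, and the nearest listed item is medical justification.

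A reader might also infer that the bias must favour the device. It need not, since recurrence-free exits shrink only the denominator and raise the rate. The shifts in the table also lie inside the planned precision of ±3.6 to ±4.4 points.

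There are safeguards. Subjects are urged to stay, following ongoing related events before exit is recommended (10.12.3), device-related events are monitored to resolution where possible (12.6), unscheduled visits assess recurrence (10.5), remote and record-based follow-up exists (10.6), and removal needs a documented rationale (10.12.4). The ineligibility and not-implanted reasons have a proper use, since every subject needs an exit form. The primary analysis is descriptive, with no hypothesis test.

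All of this stands, and it narrows the point. It does not reconcile the exit rules with the 24-month rule or recover anything that happens after exit: the advice on adverse events is only a recommendation limited to ongoing related events, and no clause protects CCS after exit.

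**Conclusion.** The contradiction between the exit rules and the 24-month rule is in the text and needs no assumption. Its consequence is limited to what follows a discretionary exit of an implanted subject: later recurrences, 12- and 24-month CCS scores, later SAEs and SADEs, and possibly informative censoring. Failures already diagnosed are not lost.

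The size cannot be fixed from the documents. Under the assumed 5 exits from 5/100, the 12-month rate moves to 5.3%, 4.2% or 3.2%. The two downward shifts, 0.8 and 1.8 points, can be set against a planning range 5.2 − 3.5 = 1.7 points wide. The bias favours the device only if exited subjects have above-average recurrence risk, which is plausible for some exits but not shown. This should be fixed, but it does not by itself invalidate the primary analysis.

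**What to change.** Reconcile Protocol 9.2, 10.12.1, 10.12.2.2, 10.12.3 and 10.12.4.

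- Keep the ineligibility and not-implanted exit reasons for subjects who did not receive the mesh.
- For subjects who did, state that recurrence, reoperation, an adverse event, missed visits or ineligibility found later do not end data collection. Only study completion, death, withdrawal of consent or loss to follow-up as defined in 10.12.5 does.
- Keep these subjects in the FAS on the 24-month schedule, by the remote or records route of 10.6 where needed, with data in the study eCRF.
- Record ineligibility found later as a major deviation that affects only the Per Protocol Analysis Set.
- Replace the sentence in 10.12.4 that leaves follow-up of withdrawn subjects to the investigator.
- State which follow-up rule applies when an intra-operative exclusion is met after the procedure was begun with the device.

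This changes data collection, not clinical care. It costs protocol wording, an edit to the exit eCRF, and a few more visits or record reviews.

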10.12.4 Withdrawal

The reason for study exit will be documented on the applicable eCRFs. In the event the subject withdraws consent during the study, the date of withdrawal will be documented. If the study Investigator(s) voluntarily removes a subject from further study participation, supporting documentation must be in place for the rationale and date of removal. Follow-up of subjects withdrawn will be determined by investigator(s). Withdrawn subjects will be not replaced.

10.12.5 Lost to Follow-up (LTFU)

Subject (LTFU) should be avoided as much as possible, and investigators are urged to do their utmost best to maintain subject follow-up compliance.

Subjects are not considered lost to follow-up until the end of the study, before the database is locked.

As is the case before documenting a missed visit, the following should take place and be documented before considering them LTFU.

- Three (3) phone calls should be made to the subject. Each attempt should be clearly documented in the source documents and the response or lack thereof should be captured.
- If there is no response to the phone calls, then an official, certified letter should be written to the subject. A copy of the letter and return or delivery receipts should be retained in the

MDT17051PDS Version 4.0 Page 32 of 56

subject's source documentation.

• In case a subject can no longer be found, the monitor shall check the appropriateness of the site's attempts to contact the subject.

Prior to final database lock, when all due diligence attempts to contact have been made, the subject is considered lost to follow-up. The Sponsor must be notified and the Exit eCRF must be completed.

11. Risks and Benefits

11.1 Potential Risks

Surgeons participating in this study are experienced with the known risks related to standard of care for hernia repair procedures. Risks associated with the use of Parietene™ DS composite include, but are not necessarily limited to: seroma, hematoma, recurrence, adhesions, bowel obstruction, fistula formation, infection, inflammation, acute and chronic pain, extrusion/erosion and/or allergic reaction to the components of the device.

The instructions for use (IFU) and training will guide surgeons on proper use of the device. Surgeons will undergo training on the device prior to participation in the study.

As with any device, there is always a risk of a rare or previously unknown side effect developing from the treatment or use of the device. Overall, the residual risk for Parietene™ DS Composite Mesh was deemed acceptable.

11.2 Potential Benefits

The information obtained from this study will be used to confirm the safety and performance of Parietene™ DS Composite Mesh in ventral hernia repair. This information may lead to findings that may or may not result in a reduction of adverse events for future subjects.

11.3 Risk Minimization

Parietene™ DS Composite Mesh was 510(k) Cleared by the FDA (USA) in June 2017. Consequently, Parietene™ DS Composite Mesh presents a favorable risk/benefit ratio to the subject. The instructions for use in addition to surgeon training, will instruct surgeons on proper use of the device to mitigate risk. There are currently no known interactions between Parietene™ DS Composite Mesh and concurrent medical interventions.

12. Adverse Events and Device Deficiencies

All information will be collected throughout the study duration, starting at the time of signing the Informed Consent. Reporting of these events to Medtronic will be occur on an AE eCRF. Each event must

Medtronic Business Restricted

MDT17051PDS Version 4.0 Page 33 of 56

be reported separately. Documented pre-existing conditions will not be considered AEs unless the nature or severity of the condition has worsened. For AEs that require immediate reporting (Table 2), initial reporting may be done by phone, fax, or on the CRF completing as much information as possible. The completed AE eCRF must be submitted to Medtronic as soon as possible. Any indication/treatment associated with the treatment of an AE must be reported.

12.1 Adverse Events

Potential Adverse Events associated with the use of Parietene™ DS composite in ventral hernia repair could include but are not limited to; seroma, hematoma, recurrence, adhesions, bowel obstruction, fistula formation, infection, inflammation, acute and chronic pain, extrusion/erosion and/or allergic reaction to the components of the device. In regard to pain, the following definitions will be used for this study:

- Acute pain (pain that resolves within three months of surgery)
- Chronic pain (pain that lasts more than three months after surgery)

For study purposes, the following occurrences are considered to be unavoidable adverse events as they are expected observations following surgical procedures (primarily associated with anesthesia) and will not be considered reportable AEs, as long as the event is not associated with significant sequelae, does not prolong hospitalization, and responds to standard medical therapy:

- Post-Operative transient nausea determined to be procedure related within the first 24 postoperative hours.
- Post-Operative transient emesis determined to be procedure related within the first 24 postoperative hours.
- Post-Operative constipation determined to be procedure and/or medication related for the duration of medication administration for management of pain.
- Post-Operative pain that the Investigator considers common and within normal limits for the procedure and is well-managed with medication.

All Adverse Events and Device Deficiencies will be collected and documented in the eCRF starting at the time of enrollment for all subjects, up to and including 24 months follow-up and monitored until resolved if possible.

For Adverse Events that require immediate reporting initial reporting may be done by phone, fax, e-mail or on the eCRF, completing as much information as is available. The original fully completed Adverse Event eCRF must be submitted to Medtronic as soon as possible. In addition, Investigators are obligated to report Adverse Events in accordance with the requirements of their IRB.

MDT17051PDS Version 4.0 Page 34 of 56

12.2 Device Deficiency

Device deficiencies (DD) information will be collected throughout the duration of the study and required to be reported to Medtronic. If there is an adverse event that results from a device deficiency, that specific event would be recorded on the appropriate Adverse Event eCRF and Device Deficiency eCRFs. If the device deficiency did not lead to an adverse event but could have led to a serious adverse device effect (i.e., if suitable action had not been taken, if intervention had been made, or if the circumstances had been less fortunate) it requires immediate reporting. Device deficiencies that did not lead to an AE should be reported on the Device Deficiency eCRF (one for each device deficiency).

In the event of a device deficiency, the device should be returned to Medtronic for analysis, if possible. Instructions for returning the study device will be provided. Device deficiencies should also be documented in the subject's medical record.

12.3 Definitions and Classifications

All definitions are provided in Table 1: Adverse Event and Device Deficiency Definitions.

Table 1: Adverse Event and Device Deficiency Definitions

Event Type	Definition
Adverse Event (AE)	Any untoward medical occurrence, unintended disease or injury, or untoward clinical signs (including abnormal laboratory findings) in subjects, users or other persons, whether or not related to the investigational medical device.
	NOTE 1: This definition includes events related to the investigational medical device and the procedures involved.
	NOTE 2: For users or other persons, this definition is restricted to events related to investigational medical devices.
Serious Adverse Event	A serious adverse event (SAE) that has:
(SAE)	a) led to death,
	b) led to a serious deterioration in the health of the subject, resulting in
	1) resulted in a life-threatening illness or injury, or
	resulted in a permanent impairment of a body structure or a body function, or
	3) in-patient or prolonged hospitalization, or
	4) medical or surgical intervention to prevent life-threatening illness or injury or permanent impairment to a body structure or a body function,
	c) led to fetal distress, fetal death or a congenital abnormality or birth defect. 10,11
	NOTE: Planned hospitalization for a pre-existing condition, or a procedure required by the clinical investigational plan, without serious deterioration in health, is not considered a SAE.
Adverse Device Effect (ADE)	An Adverse Device Effect related to the use of an investigational medical device.

MDT17051PDS Version 4.0 Page 35 of 56

Table 1: Adverse Event and Device Deficiency Definitions

Event Type	Definition
	NOTE 1: This definition includes adverse events resulting from insufficient or
	inadequate instructions for use, deployment, implantation, installation, or operation,
	or any malfunction of the investigational medical device. 10
	NOTE 2: : This definition includes any event resulting from use error or from
	intentional misuse of the investigational medical device
Serious Adverse Device	A Serious Adverse Device Effect is an adverse device effect that has resulted in any
Effect (SADE)	of the consequences characteristic of a serious adverse event
Unavoidable Adverse	An Unavoidable Adverse Event inherent to a surgical procedure that is expected to
Event	occur in all subjects for a projected duration according to the Investigator's opinion.
Device Deficiency	Inadequacy of a medical device with respect to its identity, quality, durability,
	reliability, safety, or performance.
	NOTE: Device deficiencies include malfunctions, use errors, and inadequate labeling.

